### **Safety Plans and Visits**

We have extensive experience conducting patient-oriented studies and implementing detailed safety plans. To address safety concerns associated with the study drugs, all subjects will have safety blood work performed at and in between every study visit (**Figure; visits A,B,C and black diamonds**) for serum calcium, potassium and creatinine (every 1-2 weeks +/- 3 days throughout the study). The development of hyperkalemia (considered rare since eGFR>60mL/min is an inclusion criteria), renal dysfunction, hypocalcemia, symptomatic hypercalcemia (new symptoms suggestive of memory loss or intense fatigue, or new onset constipation) or an absolute serum calcium>13.0mg/dL, will either result in disempanelment from the study to receive appropriate clinical care, or the decision to not escalate the active medical therapy. All abnormal lab values will be repeated within 1-5 days to ensure they are truly abnormal. The PI will determine, based on the severity of the abnormality, whether it can be managed with a medication dose change or will require discontinuation of medications and disempanelment. If hyperkalemia >6.5 is confirmed, the medications will be stopped and labs repeated the following day, and every 1-2 days until normalization is encountered. If milder hyperkalemia (5.4-6.5) and a substantial decline in renal function (eGFR<60 mL/min AND >25% decline in eGFR) are confirmed, the PI will lower the dose of the study drug if possible and

repeat labs in the next 1-5 days. If this occurs on the lowest dose (EPL12.5 g/d, amiloride 1.25 mg/d, placebo) and is confirmed on repeat testing, then medications will be discontinued, subject disempaneled, and labs followed to normalization as aforementioned. The use of cinacalcet can cause hypocalcemia, although the doses and duration in this study are unlikely to cause this. If calcium lower than the lower limit of reference range is encountered, the dose of cinacalcet will be lowered; if already on the lowest dose of 15mg/d, then the medication discontinued and the subject disempaneled.

If abnormal lab values (including, but not limited, to serum calcium, ionized calcium, serum potassium and serum creatinine) are encountered during the final visit 5, we will ask the participant to return for repeat labs within 1-5 days. Participants will be asked to discontinue all study medications at the end of the final visit 5, therefore the repeat labs will be performed 1-5 days after completion of the study, and it is expected that any abnormalities should resolve. If the results do not resolve, the PI will use his discretion in referring the patient to his or her provider.

All subjects will be taught how to use a home blood pressure monitor, and will be provided with a home blood pressure monitor (automated Omron cuff), since two of the study medications are mild anti-hypertensives (EPL and amiloride). Subjects using an ACEi, ARB, MR antagonist (such as spironolactone or eplerenone), or ENaC inhibitor (such as triamterene or amiloride) will undergo a washout of this medication for 2 weeks prior to study initiation, and will receive the blood pressure monitor at that time (automated Omron cuff). We anticipate the use of MR antagonists or ENaC inhibitors to be extremely infrequent or rare in this study population; however, ACEi and ARB use may be relatively common. Due to the potassium sparing effects of the possible study medications eplerenone/amiloride, subjects taking potassium supplements at the time of enrollment may also be asked to stop their potassium supplement (their potassium will be measured throughout our protocol, every 1-2 weeks, as part of our elaborate safety monitoring). Subjects will be instructed to measure their blood pressure twice daily throughout the study and report it to study staff once weekly. The PI has conducted multiple IRB approved studies with similar anti-hypertensive washout procedures safely. The target blood pressure for the study is 105-150/50-90 mmHg.

If subjects undergoing a washout experience 5 days of consecutive blood pressure readings higher than 150/90mmHg during the washout period, they will be prescribed doxazosin 2mg daily (which may be titrated up to a maximal dose of 8mg daily) to achieve a blood pressure of 105-150/50-90 mmHg. If BP is >180/90 mmHg for more than 3 consecutive days (with or without doxazosin), subjects will be evaluated in person by the PI to confirm the blood pressure levels – if confirmed, the subject will be disempaneled from the study, advised to resume their original anti-hypertensive medication, and with their consent, their primary provider will be contact to relay this important health information.

Upon initiation of the study medications (EPL, amiloride, placebo), subjects with hypertension may experience improvement of their blood pressure since EPL and amiloride are mild anti-hypertensives; subjects will continue monitoring home blood pressure to monitor for low blood pressure. If blood pressure readings fall below 105/50 mmHg for more than 2 days (unlikely), and subjects experience symptoms suggestive of hypotension (lightheaded, dizzy, tired), they will be evaluated in person to confirm their blood pressure is low and that they have related symptoms. If symptomatic hypotension is confirmed, the study drug will either be lowered, if possible, or the subject disempaneled. If subjects experience blood pressure below 90/50 mmHg, even if they report feeling well and without symptoms, we will either lower their study drug or consider disempanelment for blood pressures that are too low. Subjects who are treated with doxazosin will continue to report their blood pressure – the PI may down-titrate the dose of doxazosin once the study medications have started to maintain a blood pressure window of 105-150-50-90 mmHg.

Counseling regarding abstinence and/or contraception, in addition to pregnancy testing at every study visit (**screening, A, B, C**), will be required for women aged 18- 50 (given the potential use of EPL).

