Following a safety visit at t=2 weeks +/-3 days (see details of safety visits below), the blinded study drug may increase from the initial dose if the PI perceives the risk for hypotension to be low and as long as all safety parameters are fulfilled. The maximum dose any subject may receive is (EPL 50mg BID, amiloride 5 mg BID, placebo 1 dose BID). If the safety parameters are not within normal limits, the safety check will be repeated within 5 days and the dose may be reduced. At t=4 weeks +/- 3 days, subjects will return to the Clinical Research Center to assess outcome variables (**Figure, visit B**). Following visit B, all subjects will receive open-label cinacalcet **in addition** to continuing their blinded study drug. The initial dose of cinacalcet will be dictated by the subject's serum calcium levels and the PI's clinical judgment as it relates to reasonable safety. The initial doses of cinacalcet will range from 15 mg/d to 15 mg BID. Generally, if the subject is hypercalcemic, the initial dose will be 15mg BID, and if they are normocalcemic the dose will be 15 mg/d; however, the PI may alter this if other clinical factors indicate a more judicious approach for safety (i.e. preventing hypocalcemia). Following another safety visit 1 week +/- 3 days after cinacalcet initiation, cinacalcet may be increased to a maximum dose of 30 mg BID. If the serum calcium levels have normalized to within reference

range, it will be at the PI's discretion to increase the dose of cinacalcet, or maintain the same dose, based on the perceived risk of hypocalcemia. If the safety parameters are not within normal limits, the safety check will be repeated within 5 days and the cinacalcet dose may be reduced. Cinacalcet acts as a calcimimetic by allosteric activation of the calcium-sensing receptor and thereby decreases PTH. Cinacalcet administration to subjects with P-HPT will lower PTH and calcium, and will serve to evaluate whether the combination of EPL+cinacalcet can induce additive or synergistic reductions in PTH, when compared to those induced by placebo+cinacalcet (see *Anticipated Results*). Subjects who are instructed to increase their dose following the safety check will be told to take the blinded study drug and cinacalcet everyday at 8AM and 8PM. Subjects will return after 2 weeks +/- 3 days of cinacalcet therapy for the final study visit (**Figure, visit C**).

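### A first potassium above 6.5 triggers no required hold of blinded drug and no faster repeat; the mandatory stop waits for a confirming value that may come up to 5 days later

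*Protocol*

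**What the plan says.** The governing text is in the Protocol, Safety Plans and Visits. Calcium, potassium and creatinine are checked every 1 to 2 weeks. For any abnormal result, "All abnormal lab values will be repeated within 1-5 days to ensure they are truly abnormal". Discretion follows: "The PI will determine, based on the severity of the abnormality, whether it can be managed with a medication dose change", or whether medication must be discontinued and the subject withdrawn. The same section says that hyperkalemia leads either to withdrawal for clinical care or to a decision not to escalate.

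Two potassium tiers are then set out:

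- **Upper tier:** "If hyperkalemia >6.5 is confirmed, the medications will be stopped and labs repeated the following day, and every 1-2 days until normalization is encountered".
- **Lower tier:** "If milder hyperkalemia (5.4-6.5) and a substantial decline in renal function (eGFR<60 mL/min AND >25% decline in eGFR) are confirmed", the PI lowers the dose if possible and repeats labs within 1 to 5 days. If this recurs at the lowest dose and is confirmed, drug is discontinued and the subject withdrawn.

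Under Study Procedures (Study Drug Interventions), out-of-range safety parameters at week 2 mean that "the safety check will be repeated within 5 days and the dose may be reduced". One week after cinacalcet starts, "the safety check will be repeated within 5 days and the cinacalcet dose may be reduced". At the final visit all study drugs stop (Safety Plans and Visits).

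**The concern.** The mandatory stop for the plan's highest potassium tier depends on confirmation, and confirmation may take up to 5 days. Next-day labs, then labs every 1 to 2 days, are required only after drug has been stopped. The closest monitoring is thus prescribed once exposure has ended. While a value above 6.5 is unconfirmed and drug may still be taken, the loosest window applies.

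Two of the three arms receive a potassium-sparing drug; with 20 per arm, that is 40 of 60 subjects. The PI is blinded, so when judging whether a first value is spurious, the PI does not know whether the subject takes one of these drugs. At stake is a short period of avoidable exposure for an individual subject. No trial estimate is at stake.

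**Working it through.** The plan states no figure to reproduce. The check is a reading of the rules, followed by exposure and cost arithmetic.

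**1. Is any action required after a first value above 6.5?**

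| Provision | What it requires before confirmation |
|---|---|
| Upper-tier rule (Safety Plans and Visits) | Nothing; it starts on confirmation |
| General repeat rule (same section) | A repeat at 1 to 5 days; no shorter window for potassium |
| PI discretion by severity (same section) | Permits a dose change or discontinuation; sets no deadline |
| General hyperkalemia sentence (same section) | Withdrawal or non-escalation; non-escalation alone complies |
| Week 2 check (Study Procedures) | A repeat within 5 days; dose reduction is optional |
| Check 1 week after cinacalcet starts (Study Procedures) | A repeat within 5 days; only a cinacalcet reduction is named |
| Final visit (Safety Plans and Visits) | All drugs stop, so the gap ends |

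Not escalating and repeating on day 5 would comply with every line that applies before the final visit.

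**2. Comparison within the plan.** In Safety Plans and Visits, the instruction to lower cinacalcet when calcium is below range carries no confirmation condition. Blood pressure below 90/50 mmHg, even without symptoms, leads to a lower study-drug dose or consideration of withdrawal. The upper potassium tier therefore has the weaker written trigger.

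**3. Exposure bound.** Inputs are the 5-day end of the window, initial doses of eplerenone 12.5 mg daily to 25 mg BID and amiloride 1.25 mg daily to 2.5 mg BID, and the cap: "The maximum dose any subject may receive is (EPL 50mg BID, amiloride 5 mg BID, placebo 1 dose BID" (doses from Study Procedures).

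Formula: days × doses per day × mg per dose.

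- Number of doses: 5 × 1 = 5 once daily, or 5 × 2 = 10 BID.
- Week 2, initial doses: eplerenone 5 × 1 × 12.5 = 62.5 mg to 5 × 2 × 25 = 250 mg; amiloride 5 × 1 × 1.25 = 6.25 mg to 5 × 2 × 2.5 = 25 mg.
- Visit B and about week 5, lowest to maximum dose: eplerenone 62.5 mg to 5 × 2 × 50 = 500 mg; amiloride 6.25 mg to 5 × 2 × 5 = 50 mg.
- Maximum dose with a next-day repeat: 1 × 2 × 50 = 100 mg eplerenone or 1 × 2 × 5 = 10 mg amiloride.
- With a hold: 0.

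**4. Cost of a hold.** Formula: missed days ÷ phase length.

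| Missed days | 28-day phase | 14-day cinacalcet phase |
|---|---|---|
| 1 (spurious value, next-day repeat) | 1/28 = 3.6% | 1/14 = 7.1% |
| 2 (1 + 1, held to a further repeat) | 2/28 = 7.1% | 2/14 = 14.3% |
| 3 (1 + 2, held to a further repeat) | 3/28 = 10.7% | 3/14 = 21.4% |

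With the ±3-day visit window, one missed day is 1/31 = 3.2% to 1/25 = 4.0% of the first phase.

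**The case against.** The strongest reply is that the plan already covers this through clinical judgment. The PI chooses by severity between a dose change and discontinuation, neither that sentence nor the general hyperkalemia sentence waits for confirmation, and the repeat window opens at day 1. This stands as far as it goes. A reader might infer that drug must continue until the value is confirmed, and the documents do not say so. The PI is free to stop at once and usually would. What remains is that nothing obliges the PI to.

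A reader might also infer separate gaps in Study Procedures, because after visit B cinacalcet is added "to continuing their blinded study drug" and the later check names only cinacalcet. That reads too much into those sentences. The first describes the ordinary course and the second concerns cinacalcet titration. Safety Plans and Visits governs abnormal values at every check. There is one general omission, which Study Procedures does not close.

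Nor do the documents support calling severe hyperkalemia likely here. Risks and Discomforts lists it as common for both eplerenone and amiloride, but qualifies it as uncommon at these doses in healthy people with normal kidneys. Exclusion Criteria removes eGFR below 60 and potassium above range. ACE inhibitors and ARBs are stopped, potassium supplements may be stopped, and escalation requires acceptable safety parameters.

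Finally, the document is a summary that refers to a detailed protocol, where a stricter rule could exist. The summary does say that its risk-management algorithms are described below, and the hyperkalemia algorithm follows there. The point is limited to this text.

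**Conclusion.** The point holds as one general gap in a stated safety rule. After a first potassium above 6.5, no hold and no faster repeat is required at any on-drug check before the final visit. Discretion narrows the gap without closing it.

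The bound is 5 further days on drug. The 500 mg eplerenone or 50 mg amiloride figure needs the maximum dose, the latest permitted repeat and no action by the PI, all together. It is neither an expected exposure nor a potassium change. The documents give no event rate, so no count or harm estimate is made. The conclusion assumes that no stricter rule sits in the detailed protocol.

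This is a cheap patient-safety improvement, minor in severity, with no bearing on the validity of the analysis.

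**What to change.** In Safety Plans and Visits, add a rule for a first potassium above 6.5, applied by value alone in all three arms so that the blind is kept:

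- Hold blinded study drug and repeat potassium the same or next day.
- If the repeat is above 6.5, stop as already written.
- If the repeat is 5.4 to 6.5, keep holding, or resume only at a lower dose, with a further repeat in 1 to 2 days. This step is needed because the existing lower tier acts only when a fall in eGFR is also confirmed.
- If the subject was on the lowest dose, keep holding. If the further repeat is still 5.4 or above, discontinue and withdraw the subject, in line with the existing lowest-dose rule.
- Resume the full dose only if the repeat is below 5.4.

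Keep the 1-to-5-day window for lesser abnormalities, and cross-refer to this exception at both 5-day repeat sentences in Study Procedures.

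The cost is a short amendment and a few urgent repeat draws. A spurious first value costs about one missed day. A repeat of 5.4 to 6.5 with drug held costs 2 to 3 days, for a potassium that is still raised. The relative cost is higher in the cinacalcet phase, which carries the exploratory combination outcome; the percentages are in the working.

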  - **Visit C:** 2 weeks +/- 3 days later to assess study outcomes following cinacalcet add-on therapy. Additional safety visits are involved (black diamonds in **Figure**).

- **Study Drug Interventions:** Enrolled subjects will undergo detailed measurements of outcome variables (see detailed outcome variables below) to establish a baseline (**Figure, visit A**). All study visits will be conducted in the morning, following at least 1 hour of monitored supine rest in the Clinical Research Center. Following study visit A, subjects will be randomized to the blinded study drug by the BWH Research Pharmacies. The initial dose of the blinded study drug will be dictated by the subject's blood pressure and the PI's clinical judgment as it relates to reasonable safety. Subjects with blood pressures near the lower range of our safety margin of 105/50 mmHg will receive the lowest dose, and subjects with higher blood pressures (or known hypertension) will receive a higher dose. The initial doses will range from: eplerenone (EPL) 12.5 mg/d to 25 mg/BID, amiloride 1.25 mg/d to 2.5 mg/BID, or placebo. The EPL arm represents the active intervention: a direct MR antagonist. The placebo arm represents a negative control. Since EPL is expected to influence more than just PTH (EPL will also decrease blood pressure and urinary excretion of potassium and calcium) when compared to placebo, the amiloride intervention represents a *second control* to provide insights into the *mechanism* by which EPL may influence PTH. Like EPL, amiloride is a potassium-sparing diuretic, with mild anti-hypertensive and hypocalciuric effects, and will therefore induce similar changes in blood pressure and urinary potassium/calcium excretion. Unlike EPL, amiloride does not directly block the MR. Rather, it blocks epithelial sodium transport channels (ENaC) in the renal distal tubule (and vascular epithelium).

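### Home blood pressure reaches staff once a week, so a reading below 90/50 that the protocol acts on even without symptoms can go unseen for up to 6 days

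*Protocol*

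**What the plan says.** Under Safety Plans and Visits the protocol states: "Subjects will be instructed to measure their blood pressure twice daily throughout the study and report it to study staff once weekly". After study drug starts, home readings continue for the stated purpose of detecting low pressure.

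The same section then sets limits for action. The one at issue opens "If subjects experience blood pressure below 90/50 mmHg, even if they report feeling well and without symptoms"; staff then either reduce the study drug or consider withdrawing the subject. The rule does not say whether one reading is enough, and it sets no response time. The other limits need a run of readings: more than 2 days below 105/50 together with symptoms, more than 3 consecutive days above 180/90, or 5 consecutive days above 150/90 during washout.

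Under Study Procedures, the first scheduled contact after drug start is the 2-week safety visit ("Following a safety visit at t=2 weeks +/-3 days"), at which the dose may be raised. Visit B follows at 4 weeks +/- 3 days, a further safety visit 1 week +/- 3 days after cinacalcet starts, and visit C 2 weeks +/- 3 days after it starts. Blinded drug continues to visit C.

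Nothing in the supplied text gives a threshold for calling in, an instruction to contact staff between reports, or automatic transmission of readings.

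**The concern.** The below-90/50 rule deliberately covers subjects who feel well. In those subjects symptoms will not prompt a call. The subject sees the reading at once, but the dose decision rests with staff, and the only stated route to staff is weekly. Followed as written, the rule can be applied days after its condition is met, while the subject goes on taking the same dose of eplerenone or amiloride.

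The gap falls partly in the period of dose increase: after the week-2 visit the dose can rise to as much as eplerenone 50 mg BID or amiloride 5 mg BID, and no visit is scheduled until week 4. Some washout subjects may also be on doxazosin (up to 8 mg daily) when study drug starts, with reduction afterwards at the investigator's discretion. The protocol lists hypotension as a risk of all of these drugs.

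What is at stake is subject safety at the margin, not inference. Nothing here touches the PTH comparison, the type I error or the power.

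**Working it through.** The plan states no detection delay, so there is no figure of its own to reproduce.

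**Inputs.** From the protocol: weekly reporting, twice-daily measurement, the action limits and the visit windows. Assumed: a fixed 7-day interval with the report at the end of day 7, a low reading equally likely on each day, and no voluntary call in between.

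**1. Weekly reports alone.** For a reading on day s of the reporting week, delay = 7 − s.
- s = 1 to 7 gives 6, 5, 4, 3, 2, 1, 0 days.
- Mean = 21/7 = 3.0; maximum 6; 3 of the 7 days wait 4 days or more.
- On a half-day grid (0, 0.5, …, 6.5) the mean is 3.25. In continuous time (0 to 7) it is 3.5.
- If confirmation on the next day were required, with both readings in one reporting week, the delays are 5, 4, 3, 2, 1, 0: mean 15/6 = 2.5, maximum 5.

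**2. Doses taken meanwhile, after the day of the reading.** Once daily: up to 6 × 1 = 6, mean 3. BID: up to 6 × 2 = 12, mean 6.

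**3. Spacing of scheduled visits.**

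| Interval | Calculation | Days |
|---|---|---|
| Drug start to week-2 visit | 14 ± 3 | 11–17 |
| Week-2 visit to visit B (day 25–31) | 25 − 17 to 31 − 11 | 8–20 |
| Cinacalcet start to its safety visit | 7 ± 3 | 4–10 |
| That visit to visit C (day 11–17 of cinacalcet) | 11 − 10 to 17 − 4 | 1–13 |

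Before visit B, visits are always further apart than the weekly reports. In the cinacalcet phase they may be closer, so they fill the gap only in part.

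**4. Delay if staff also review home readings at visits.** A visit on day j of a reporting week shows the readings of days 1 to j earlier by 7 − j days, a saving of j(7 − j) days of delay, at most 12 (j = 3 or 4).
- Whole treatment period, nominal visits on days 14, 28, 35 and 42: without visits the delays sum to 42 × 3 = 126. The best case is (126 − 4 × 12)/42 = 1.86. If visits fall on the report day they save nothing: 126/42 = 3.0. The average over the seven possible report days is 2.24.
- Up to visit B only, reports on days 7, 14, 21 and 28 and visits anywhere in their windows: (84 − 2 × 12)/28 = 2.14 at best, 84/28 = 3.0 at worst.
- The maximum stays 6 in both cases, because at least one reporting week contains no visit.

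**5. Run-based limits.** If a rule is met on the k-th day of a run lying within one reporting week, the added delay is at most 7 − k: 4 days for below 105/50 (k = 3), 3 for above 180/90 (k = 4), 2 for above 150/90 in washout (k = 5). These rules are affected less than the below-90/50 rule. Longer delays arise only when an earlier report already showed staff part of the run.

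**The case against.** The strongest objection is that absence cannot be shown from this text. The document is a protocol summary that refers to a Detailed Protocol, and the consent pages were not available. An instruction to telephone about a low reading would naturally sit there or on the blood pressure log. This stands: the point can be made only about the supplied text.

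Second, 0 to 6 days with mean 3.0 simply restates weekly reporting; it measures delay, not harm. This also stands. The documents give no rate of readings below 90/50, so the number of subjects affected cannot be estimated.

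Third, the plan already limits the risk. It says "Subjects with blood pressures near the lower range of our safety margin of 105/50 mmHg will receive the lowest dose"; a dose increase requires the investigator to judge the risk of hypotension low; heart failure and prior infarction or stroke are excluded; and both drugs are described as mild anti-hypertensives. The figure of 12 BID doses is therefore a worst case. The low-pressure rule is also discretionary and sets no urgent timetable. All of this lowers the importance of the point, but none of it gives staff the reading sooner.

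Two stronger readings are tempting and are not supported:
- A reader might set the weekly report against "All abnormal lab values will be repeated within 1-5 days to ensure they are truly abnormal" and infer that blood pressure is watched less closely than laboratory values. The two are not alike. The 1–5 days is confirmation time once staff hold an abnormal result. Detection of a laboratory abnormality itself waits for draws every 1–2 weeks +/- 3 days, so weekly pressure reports are about as frequent or more so.
- A reader might infer that scheduled visits never help because they are always more than a week apart. That is true only before visit B.

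**Conclusion.** The point holds as a cheap safety improvement of low probability, not as a proven error. On the supplied text, a reading below 90/50 can go unseen by staff for 0 to 6 days: mean 3.0 on weekly reports alone, about 2 to 3 if readings are also reviewed at visits, maximum still 6. This rests on a fixed 7-day interval with the report at its end, a uniform day of occurrence, and no call in between. Half-day or continuous timing gives a mean of up to 3.5 and a maximum of 6.5 to 7 days, which does not change the conclusion.

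A reader might go further and infer that the trial has no call-in route at all, or that weekly review is unsafe for subjects who feel well. The documents support neither: the materials most likely to hold such an instruction were not supplied, and no event rate is given. Nor is there reason to single out the above-180/90 limit, since the run-based rules lose less time than the below-90/50 rule.

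**What to change.** Keep the weekly report. Add to Safety Plans and Visits, and to the subject's blood pressure log, wording such as:

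*A subject with a home reading below 90/50 mmHg repeats it once the same day. If the repeat is also below 90/50, the subject contacts study staff that day, and the repeated reading triggers the dose-reduction or withdrawal rule.*

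This brings the delay for a confirmed reading to about 0 days and settles whether one reading is enough. Optionally, ask subjects to call as well when a run meets one of the other limits in the section. If the Detailed Protocol, consent form or subject materials already contain such an instruction, a cross-reference is all that is needed.

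The cost is one or two sentences and some extra unscheduled calls, including false alarms, which the repeat reading limits. No threshold, treatment rule, scheduled visit or analysis changes.
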